#### **Assessment of lung nodules with low dose CT scan at MDACC**

Investigations will be performed with low-dose CT scans (average effective dose <1.5 mSv, without contrast medium), with a multidetector (64 slices) CT scanner (CT750 HD, General Electric Healthcare, USA) with the following parameters:

- 120 Kvp, noise modulation, Radiation dose < 3mGy for standard size patient.

Matrix 512x 512

- 2.5 mm, 1.25 mm and 0.625 mm thickness

Soft tissue and lung algorithm

- single breath, in respiratory apnea
- retro-reconstruction at 50% interval
- multiplannar reconstruction at scanner.3-dimensional volume reconstruction performed with dedicated software .

#### **Assessment of lung nodules with standard chest CT**

Investigations will be performed with standard CT scans (with or without contrast medium), with multidetector scanner(16 or 64 slices):

- 120 Kvp.

Matrix 512x 512

- 2.5 mm thickness

Soft tissue and lung algorithm

- single breath, in respiratory apnea
- retro-reconstruction at 1.25 slice interval
- multiplannar reconstruction at scanner.3-dimensional volume reconstruction performed with dedicated software .

## 8. CRITERIA FOR EVALUATION AND ENDPOINT DEFINITION

### 8.1 Primary Endpoint

For the purposes of the primary endpoint, only sub-solid (non-solid or partially solid) nodules will be assessed. Target lesions are defined as non solid or partially solid nodules persistent at least after 3 months follow up with standard or low dose CT scan, at least 4 mm in size. Non target lesions include solid nodules (larger than 3.5 mm), new lesions at baseline (e.g., that were not present on prior CT) or non-solid or partially solid nodules < 4mm in size.

The primary end-point will be the difference in sum of longest diameters of baseline target lesions in a person-specific analysis. New subsolid lesions identified during follow-up satisfying the same criteria for the definition of target lesion will also be included in the analysis.

It has been assumed a -0.2 mm average reduction of the sum of the longest diameter of all non-solid and partially-solid lesions at 12 months with respect to baseline in the placebo arm and an expected average reduction of -1.0 mm in the aspirin group.

### 8.2 Secondary Endpoints

We will investigate the effects of aspirin on the following secondary end points: (see paragraph 13.5 for a detailed statistical analysis):

*Evaluation of response according to modified RECIST criteria:*

The per-lesion analysis will be done according to the Modified RECIST criteria:

Complete Response (CR)= disappearance of the lesion

Partial Response (PR) = shrinkage of  $\geq 30\%$  of the longest diameter

Stable Disease (SD) = anything other than CR, PR or PD

Progressive Disease (PD) = growth  $\geq 20\%$ , with a minimum increase of 2 mm

The per-subject analysis will be done according to Modified RECIST criteria:

For single nodules a clinical meaningful shrinkage of 30% or more of the longest diameter will be considered as a treatment success after one year of treatment as long as there are no new non-solid or partially solid nodules or nodules highly suspicious for malignancy or shown to be malignant (modification to RECIST criteria). Growth of 20% or more with a minimum of 2 mm, will be considered progression.

For multiple lesions the sum of the maximum diameters of all target nodules will be considered, using the same parameters to define success and progression (30% or more decrease and 20% or more increase, respectively).

In case of multiple lesions, treatment will be considered successful when a complete response (CR) or partial response (PR) occurs according to modified RECIST criteria, while treatment will be considered a failure when progression of disease (PD) or stable disease (SD) occurs according to the same criteria. Specifically:

CR: disappearance of all target lesions, + no progression of non-target lesions + no appearance of new non-solid or partially solid lesions, and no appearance of new nodules highly suspicious for malignancy

or shown to be malignant (even if solid);

PR: CR for some target lesions + PR/SD for other target lesions + no PD or new lesions as described in CR above; or, PR (i.e.,  $\geq 30\%$  decrease in the sum of the longest diameter of target lesions, taking as reference the baseline sum longest diameter) for target lesions + no PD for non target lesions + no appearance of new lesions as described in CR above;

PD: PD (A  $\geq 20\%$  increase in the sum of the longest diameter of target lesions, taking as reference the smallest sum longest diameter recorded since the start of treatment) for target lesions irrespective of response of non target lesions; or PD for non target lesions irrespective of response for target lesions; or appearance of new non-solid or partially solid lesions or appearance of new nodules highly suspicious for malignancy or shown to be malignant irrespective of response of target or non target lesions;

SD: neither sufficient shrinkage to qualify for PR nor sufficient increase to qualify for PD, taking as reference the smallest sum longest diameter since the start of treatment.

All solid nodules will be considered in a separate secondary analyses, unless they are highly suspicious for malignancy or are actually shown to be malignant, in which case they will represent progressive disease (PD). Non-suspicious (stable solid nodules with clearly benign features) will not be considered in the analysis according to RECIST criteria

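### Section 8.2 sets different per-subject response rules for single and multiple nodules, so the same new subsolid nodule is progression in one participant and has no category in another

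*Combined protocol and SAP*

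**What the plan says.** Section 8.2 first gives a per-lesion rule, in which PD is growth of at least 20% with an increase of at least 2 mm. It then gives two per-subject rules.

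- **Single nodules.** Shrinkage of 30% or more is a success "as long as there are no new non-solid or partially solid nodules or nodules highly suspicious for malignancy or shown to be malignant". Then: "Growth of 20% or more with a minimum of 2 mm, will be considered progression". This paragraph defines only success and progression, and it does not mention non-target lesions.
- **Multiple lesions.** The sum of the target diameters is judged "using the same parameters to define success and progression (30% or more decrease and 20% or more increase, respectively". A CR/PR/PD/SD list follows, introduced by "In case of multiple lesions, treatment will be considered successful when a complete response (CR) or partial response (PR) occurs"; conversely, "treatment will be considered a failure when progression of disease (PD) or stable disease (SD) occurs". PR through the sum also requires "no PD for non target lesions + no appearance of new lesions as described in CR above". PD is a 20% increase in the sum, "taking as reference the smallest sum longest diameter recorded since the start of treatment", or PD of non-target lesions, "or appearance of new non-solid or partially solid lesions or appearance of new nodules highly suspicious for malignancy" (or shown to be malignant), whatever the other lesions do. No 2 mm minimum appears in this list.

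The closing paragraph of 8.2 adds that solid nodules that are highly suspicious or proven malignant represent PD. That sentence is not restricted to multiple lesions.

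**The concern.** A per-subject response category should mean the same thing for everyone in the table. Here three events are handled according to how many nodules the participant has: a new subsolid nodule, progression of a non-target lesion, and a small relative increase below 2 mm. Two analysts following the text could classify the same participant differently, and the reported progression rate would depend partly on the mix of single-nodule and multiple-nodule participants. On one reading of single nodules, the success rate would too.

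**Working it through.** The plan states no figure for this rule, so there is none to reproduce. The check applies both rules as written to the same changes. Inputs from 8.2 are the 30% and 20% thresholds, the 2 mm minimum, and the new-lesion and non-target triggers. Inputs from 8.1 are the 4 mm minimum for a target and the classing of subsolid nodules under 4 mm as non-target.

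| Change in target diameter or sum | Other event | Single-nodule rule | Multiple-lesion rule |
|---|---|---|---|
| 8 to 8 mm (0%) | new subsolid nodule | not success, not PD, no category | PD |
| 8 to 5 mm (-3/8 = -37.5%) | new subsolid nodule | not success, not PD, no category | PD |
| 8 to 8 mm (0%) | new solid nodule, highly suspicious or malignant | PD (closing paragraph) | PD |
| 8 to 5.5 mm (-2.5/8 = -31%) | 3 mm subsolid nodule grows to 6 mm | success, if single means one target | PD |
| 8 to 9.6 mm (+1.6/8 = +20%) | none | not PD (1.6 mm is under 2 mm) | PD as written; SD if the minimum applied |
| 10 to 12 mm (+2/10 = +20%) | none | PD | PD |
| 8 to 5 mm (-37.5%) | none | success | PR, hence success |

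**New subsolid nodule (rows 1 and 2).** The single-nodule rule denies success. The multiple-lesion rule gives PD, which is failure. Neither participant is a success, so the difference lies only in the PD category.

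**Non-target growth (row 4).** The 3 mm nodule increases by 3/3 = 100% and by 3 mm, so it is PD under the per-lesion rule. The single-nodule paragraph has no non-target condition, so all its stated conditions for success are met. Here the success result changes as well as the label, but only if a single nodule means one target lesion.

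**The 2 mm minimum (row 5).** Two millimetres exceeds 20% of the diameter when the diameter is below 2/0.20 = 10 mm. A single nodule must therefore grow by 2/4 = 50% from 4 mm, 2/5 = 40% from 5 mm, or 2/8 = 25% from 8 mm. Two targets of at least 4 mm have a baseline sum of at least 8 mm. Measured from baseline, the missing minimum therefore matters for sums from 8 mm to just under 10 mm. If an optional month 3 or month 6 CT shows a smaller sum, that sum becomes the reference and may be below 8 mm.

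**The case against.** The strongest reply is that one common rule was intended. A participant with one target and a non-target or new nodule has more than one lesion, and could be placed under the multiple-lesion list. On that reading the single-nodule paragraph omits non-target lesions because there are none. This is a fair reading, and it makes the non-target example depend on interpretation. But 8.2 does not say so, and it describes multiple lesions through the sum over target nodules, which points towards counting targets. It could also be said that using the same parameters carries the 2 mm minimum across. The parenthesis that spells those parameters out contains only the 30% and 20% thresholds, and the PD definition for the sum repeats only the 20%.

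A reader might infer four stronger points, which the documents do not support:

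- **That a new malignant nodule escapes PD in a single-nodule participant.** The closing paragraph of 8.2 makes highly suspicious or malignant solid nodules PD for everyone, and 8.2 also plans a cancer rate per arm. The gap concerns new subsolid nodules.
- **That a new subsolid nodule changes success or failure.** It does not, as rows 1 and 2 show.
- **That the number of lesions is ignored in the analysis.** Section 13.2 does not use it in randomization but says it will enter a stratified analysis. Sections 13.4 and 13.5 do not list it.
- **That a definite number of progressions is missed.** Assuming 50-80% single-nodule participants and 10% with a new nodule would give 0.5 x 10% = 5 to 0.8 x 10% = 8 percentage points. Neither input is in the documents. The product would also be an upper figure, since some of those participants would be PD anyway through growth or a suspicious solid nodule.

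It also stands that the rules apply equally to both arms of a blinded randomized trial, so no between-arm bias is shown, and that 8.2 analyses new nodules separately.

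**Conclusion.** The inconsistency is real on the wording of 8.2. A new subsolid nodule is PD with multiple lesions and has no category with a single nodule; this affects the PD category and any progression rate, not success or failure. Non-target progression can change success itself, provided that a single nodule means one target lesion. The 2 mm minimum is missing from the sum-based rule, which matters for reference sums below 10 mm.

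The effect is on a secondary endpoint. Its size cannot be taken from the documents, which give neither the share of single-nodule participants nor the frequency of new subsolid nodules. The primary endpoint in 8.1 is a change in summed diameters that does not use these categories, and the sample size in 13.3 rests on that change, so both are unaffected.

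**What to change.** Replace the two per-subject rules in 8.2 with one CR/PR/SD/PD definition for every participant, whatever the number of target nodules. With one target, the sum is simply its diameter. New subsolid nodules, new highly suspicious or malignant nodules, and non-target progression then count the same way for all, and so does the reference measurement for PD.

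Carry the 2 mm minimum increase into the sum-based PD rule. Deleting the single-nodule paragraph without doing so would make 4 to 4.8 mm (+0.8/4 = +20%) progression.

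The cost is a short rewrite of 8.2, settled before unblinding, and a derivation from lesion data already collected; no extra scans are needed. The reported progression rate may be slightly higher, although the minimum works the other way for sums under 10 mm. The success rate may be slightly lower if non-target growth had been disregarded for participants with one target.

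### Section 8.2 gives two incompatible rules for per-subject partial response with multiple nodules, so the same participant can be a success under one and a failure under the other

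*Combined protocol and SAP*

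**What the plan says.** All of this stands in section 8.2 of the combined protocol and SAP, under the modified RECIST criteria.

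- **Opening rule for multiple lesions:** "For multiple lesions the sum of the maximum diameters of all target nodules will be considered, using the same parameters to define success and progression". The thresholds are a decrease of 30% or more for success and an increase of 20% or more for progression.
- **What success means:** "treatment will be considered successful when a complete response (CR) or partial response (PR) occurs according to modified RECIST criteria", whereas "treatment will be considered a failure when progression of disease (PD) or stable disease (SD) occurs according to the same criteria".
- **First limb of per-subject PR:** "PR: CR for some target lesions + PR/SD for other target lesions", with no PD and no new lesions, referring back to the CR definition. No condition on the sum is attached.
- **Second limb, joined by *or*:** a 30% or greater "decrease in the sum of the longest diameter of target lesions, taking as reference the baseline sum longest diameter", with no non-target progression and no new lesions.
- **Per-lesion categories:** complete response (CR) is disappearance. PR is shrinkage of at least 30%. Progressive disease (PD) needs growth of at least 20% and also at least 2 mm. SD is whatever is left.
- **Per-subject PD and SD:** both refer to the summed diameter. PD is a rise of at least 20%, and SD lies between PR and PD.

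**The concern.** The opening rule and the first limb measure different things. One asks how far the total has fallen. The other asks whether any single lesion has gone while no other has progressed. When the lost nodule is a small part of the total, the first limb is met and the sum rule is not.

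Section 8.2 counts PR as success and SD as failure, so the disagreement decides whether a participant is a responder. Two programmers could derive different responder counts from the same scans, and the choice could be made after results are known. Section 13.4 also places participants without a final CT in a failure group, and section 8.2 is the only place where success and failure are defined.

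**Working it through.** **The plan's own figure first.** Section 13.3 gives a difference of 0.8 mm, a standard deviation of 1.6 mm, two-sided alpha 0.05 and 80% power with a two-sample t-test. The effect size is 0.8/1.6 = 0.5. The noncentral t calculation gives 63.8, so 64 per arm and 128 in total, with power 80.1%. The figure reproduces. It rests on the continuous change in the sum, so nothing below alters it.

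**Inputs.** Target lesions are at least 4 mm (section 8.1). Nodules above 10 mm are eligible when the volume doubling time exceeds 400 days (section 4.1.4). The response rules are those of section 8.2.

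**Assumptions for the examples.** Lesion sizes are hypothetical. There is no non-target progression and no new lesion, and month 12 is the only follow-up CT, so the smallest earlier sum is the baseline sum.

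**Formula.** Change in sum = (sum at month 12 − sum at baseline) / sum at baseline.

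| Baseline (mm) | Month 12 (mm) | Sum (mm) | Change | Lesion categories | First limb | Sum rule |
|---|---|---|---|---|---|---|
| 4, 9 | 0, 9 | 13 to 9 | −30.8% | CR, SD | PR | PR |
| 4, 10 | 0, 10 | 14 to 10 | −28.6% | CR, SD | PR | SD |
| 4, 10, 10 | 0, 10, 10 | 24 to 20 | −16.7% | CR, SD, SD | PR | SD |
| 4, 12, 12 | 0, 14.3, 14.3 | 28 to 28.6 | +2.1% | CR, SD, SD | PR | SD |
| 4, 8, 8, 8 | 0, 9.9, 9.9, 9.9 | 28 to 29.7 | +6.1% | CR, then SD | PR | SD |
| six of 4 | 0, five of 5.9 | 24 to 29.5 | +22.9% | CR, then SD | PR, if the no-PD condition omits the sum | PD |

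**Where the rules part without any growth.** If a 4 mm nodule vanishes beside one unchanged nodule of size b, the sum rule is met when 4/(4 + b) ≥ 0.30, so b ≤ 4/0.30 − 4 = 9.3 mm. With k equal nodules, one gone and the rest unchanged, the fall is 100/k percent: 33.3% for three, 25% for four. Two lesions of unequal size, or four equal ones, are therefore enough for conflict.

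**Why the remaining lesions are SD in the growth rows.** 14.3/12 is +19.2%, below 20%. The rise from 8 to 9.9 mm and from 4 to 5.9 mm is 1.9 mm in each case, below 2 mm, although in percent it exceeds 20.

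**How unusual growth of the sum is.** Without becoming PD, a lesion of 10 mm or less can grow by just under 2 mm, and a larger one by just under 20%. To outweigh a lost 4 mm nodule, the others must grow by more than 4 mm in total.

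- With one other lesion, 0.20 × b > 4, so b must exceed 20 mm.
- With two others, at least one must exceed 10 mm, since two lesions of 10 mm or less together gain less than 4 mm.
- With all others at 10 mm or less, at least three must grow.

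**What the no-PD condition excludes.** The first limb already requires every target lesion to be CR, PR or SD, so the condition adds either non-target progression or progression of the sum. It points back to the CR definition, which mentions progression only for non-target lesions. If it covers the sum, the last row is excluded, but the +2.1% and +6.1% rows remain PR. If it does not, a participant can meet PR and PD together.

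**The case against.** The strongest defence is that the first limb is deliberate. The criteria are labelled as modified RECIST. The opening sentence is general, and the itemised definitions that follow are more specific and join two limbs by *or*. Disappearance of a persistent subsolid nodule with no progression elsewhere could be a meaningful response in a chemoprevention trial, and the guard against progression and new lesions limits abuse. This reading is fair, and the documents do not rule it out. It does not remove the inconsistency, because the opening sentence still judges success by the sum alone. It does mean that deleting the limb is not the only acceptable repair.

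Three stronger inferences are tempting and should not be drawn.

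- **That the rule biases the response difference toward the null, for instance because a faint 4 mm nodule is missed on a 2.5 mm section.** This assumes that first-limb responders are misclassified. If aspirin clears small nodules, the limb captures real effect. The documents give no disappearance rate by arm and no false-disappearance rate. Target lesions must have persisted for at least three months, the CT procedure must be the same at both time points, and images are also reconstructed at finer intervals (section 7.6).
- **That growing disease is routinely scored as success.** Growth of the sum needs the particular patterns set out in the working.
- **That the trial's main result is at risk.** The primary endpoint is the change in the summed diameter in millimetres (section 8.1).

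**Conclusion.** The point stands as an internal inconsistency in a secondary endpoint. As written, section 8.2 can classify the same multi-nodule participant as PR and as SD. This needs only two lesions and no growth: −28.6% for 4 and 10 mm, −16.7% for 4, 10 and 10 mm. PR with a larger sum is possible but less common (+2.1% and +6.1% in the examples). Overlap of PR with PD (+22.9%) arises only if the no-PD condition leaves out the sum.

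The conclusion rests on the wording of the rules and on illustrative lesion sizes within the eligible range. It concerns only participants with two or more target lesions. Because their number is not given, no effect on response rates can be stated.

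**What to change.** Before unblinding, define per-subject PR for multiple lesions by the sum rule alone: a fall of 30% or more from the baseline sum, no non-target progression and no new lesions. Either remove the first limb or make it subject to that threshold. Report disappearance of individual nodules in the per-lesion analysis, which already has a category for it. This brings PR into line with the opening sentence, the per-subject SD rule and the sum-based primary endpoint.

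If the sponsor intended the composite, amend the opening sentence to name both limbs, state that the no-PD condition includes progression of the sum, and report the sum-only responder rate beside the composite rate.

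The cost is endpoint wording and the matching derivation code. Under the first option, some participants with one vanished nodule and an otherwise stable sum will no longer count as responders. How many cannot be estimated from the documents.

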#### *Analysis of non target lesions*

Evaluation of number and size of non target lesions before and after treatment including :

-Subsolid nodules less than 4 mm .

-Solid nodules: evaluation of number and size of preexisting or new solid nodules will be performed. The analysis will be analogous to the analysis of non-solid and partially solid nodules described above, but substituting solid lesions for subsolid lesions. In addition, a combined analysis of nonsolid and solid lesions (with solid lesions considered to be non-target lesions) will be performed.

- New nodules: A separate analysis examining new nodule appearance at 0 and 12 months

- Cancer: the rate of cancer in each arm will be assessed.

#### *Nodule density*

We will evaluate nodule density measured by quantitative changes in mean and maximum Hounfields Unit (HU) before and after treatment.

#### *miRNA*

The effectiveness of the miRNA serum protocol will be evaluated by comparing the sensitivity, specificity and accuracy of miRNA to identify patients with GGO or with partially solid nodules and to predict aspirin treatment response considering the LDCT screening protocol as the reference procedure.

The ultimate goal is to evaluate if miRNA analysis in the serum can represent a new non-invasive test to identify patients with GGO or with partially solid nodules and to predict treatment response to low-dose aspirin.

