## 1. OBJECTIVES

**1.1 Primary Objectives** – The primary objective is the evaluation of the effect of Aspirin as a chemopreventive agent for lung cancer. Particularly, the efficacy of Aspirin in reduction of size and number of CT-detected lung subsolid nodules will be evaluated in high-risk asymptomatic subjects currently undergoing CT screening programs at the European Institute of Oncology (EIO) and at MD Anderson Cancer Center (MDACC).

In addition, we will include subjects undergoing CT outside the context of a screening program with a subsolid nodule confirmed by pulmonary CT scan (qualifying scan).

The efficacy will be evaluated in a person-specific analysis.

**1.2 Secondary Objectives** – Secondary objective of the study will be the modulation of biological markers after treatment and the correlation of these findings with modification of lung nodules diameters. In particular we will evaluate the effect of Aspirin on a signature of serum microRNA correlated to subsolid nodules. Other secondary endpoints will be the per-lesion analysis including the evaluation of lung nodule density before and after treatment, the number and size of non target lesions including solid nodules and evaluation of response according to modified RECIST criteria. Additional biomarkers will include the modulation of ultrasensitive circulating hs-CRP, the evaluation of urinary cotinine as marker of tobacco exposure and investigation of the potential effect of aspirin according to its concentration, the measurement of urinary prostaglandin metabolites (PGEM) and leukotriene (LTE4), both normalized normalized to urinary creatinine concentration. Serum concentration of thromboxane B2 (TXB2) will be determined as a measure of compliance. We will also evaluate the tolerability of Aspirin at dose of 100 mg/day.

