### 3. SUMMARY OF STUDY PLAN

We will conduct a double-blind placebo-controlled phase IIb study in which participants will be randomized to receive either Aspirin (100 mg/day) or placebo for 12 months.

A total of 128 subjects will be accrued (randomized to drug or placebo); 64 per arm in a 3.5 year time period.

Participants will be men and women, current or former smokers, with undetermined subsolid lung nodules detected at low dose screening CT scan (without contrast medium) running at the EIO and MDACC. In addition, we will include subjects undergoing CT outside the context of a screening program, providing a subsolid nodule confirmation by a CT scan. Participants will be given 100 mg Aspirin daily or placebo for 12 months.

The primary endpoint will be the shrinkage of GGO and partially solid lung nodules after one-year treatment per-subject analysis.

Secondary endpoints will be the modulation of biological markers after treatment and the correlation of these findings with modification of lung nodules diameters. In particular we will evaluate the effect of Aspirin on a signature of serum miRNA correlated to subsolid nodules. Other secondary endpoints will be the per-lesion analysis including the evaluation of lung nodule density before and after treatment and the number and size of non target lesions. Additional biomarkers will include the modulation of hs-CRP, the evaluation of urinary cotinine as marker of tobacco exposure and investigation of the potential effect of aspirin according to its concentration, the measurement of urinary prostaglandin metabolites (PGEM) and urine leukotriene E4 (LTE4) both normalized to urinary creatinine concentration. Serum concentration of thromboxane B2 (TXB2) will be determined as a measure of compliance. We will also evaluate the tolerability of Aspirin at dose of 100 mg/day.

Complete physical exam and safety lab tests will be performed at 0, 6 and 12 months. Phone contact will occur at month 1, 3, 9 and 13 (i.e, one month after treatment completion).

Biomarkers: blood and urine will be collected at 0, 6 and 12 months

Lung lesions will be measured with a CT scan at 0 and 12 months. Both standard dose and low dose CT scans are allowed provided that the same procedure is used at both time points.

Duration of study will be five years: 3.5 years of accrual, one year of treatment and 0.5 year for biomarkers measurement.

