#### *Additional biomarkers*

Additional biomarkers will include the modulation of hs-CRP as marker of inflammation, the evaluation of urinary cotinine as marker of tobacco exposure and investigation of the potential effect of aspirin according to its concentration, the measurement of urinary PGEM and LTE4 normalized to urinary creatinine concentration. Serum TXB2 will be determined as a measure of compliance. Results will be compared between the two treatment arms (aspirin and placebo).

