## 13.5 Secondary Objectives, Endpoints, Analysis Plans

Generalized linear mixed models for longitudinal data will be used to compare the study groups using the standard general model  $y = X\beta + Zu + \epsilon$ , with  $y$  the response variable (e.g. secondary endpoint variable),  $X$  and  $\beta$  the design matrix and unknown parameters for the fixed effects and  $Z$  the design matrix for the random effects and  $u$  the random effects. Treatment arm (aspirin or placebo) and time visit (baseline, 6 and 12 months) will be considered fixed effects, smoking history and age at study entry random effects. Secondary endpoints include a per-lesion analysis by nodule type. Identity and logit link functions will be used for normal and binary data respectively. All tests will be two-sided and considered significant at the 5% level.

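### Section 8.2 defines the miRNA endpoint as test accuracy, which does not measure the aspirin effect on the signature that sections 1.2 and 3 promise

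*Combined protocol and SAP*

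**What the plan says.** Section 1.2 puts miRNA under the secondary objective of "modulation of biological markers after treatment and the correlation of these findings with modification of lung nodules diameters" and continues: "In particular we will evaluate the effect of Aspirin on a signature of serum microRNA correlated to subsolid nodules". Section 3 repeats it: "In particular we will evaluate the effect of Aspirin on a signature of serum miRNA correlated to subsolid nodules".

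Section 8.2 opens with "We will investigate the effects of aspirin on the following secondary end points" and refers to 13.5 for the analysis. Its miRNA paragraph reads "The effectiveness of the miRNA serum protocol will be evaluated by comparing the sensitivity, specificity and accuracy of miRNA to identify patients with GGO", and the sentence goes on "or with partially solid nodules and to predict aspirin treatment response considering the LDCT screening protocol as the reference procedure". The paragraph ends with the aim of a non-invasive blood test for these two purposes. It gives no score, no comparison of arms and no sampling time. The next paragraph, on hs-CRP, cotinine, PGEM, LTE4 and TXB2, does state a contrast: "Results will be compared between the two treatment arms (aspirin and placebo".

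Section 13.5 gives one general mixed model for secondary endpoints: "Treatment arm (aspirin or placebo) and time visit (baseline, 6 and 12 months) will be considered fixed effects". It names neither miRNA nor any analysis of sensitivity or specificity. The footnote to the schedule of events limits miRNA sampling to baseline and month 12.

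**The concern.** An effect of aspirin on a signature is a between-arm difference in a marker. Sensitivity, specificity and accuracy describe how well a test agrees with CT. They use different outcome variables and different comparisons, so carrying out 8.2 faithfully would leave the question in 1.2 and 3 unanswered.

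The missing outcome variable also leaves room for choice after the data are seen. Section 2.3 speaks of a signature of 34 microRNAs, the biomarker rationale reports a risk score, and section 9.1 plans to assay about 850 miRNAs.

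Finally, accuracy is a poor fit to this population. Every participant is selected for having the condition that the test is meant to detect.

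**Working it through.** **1. The plan's own figures.** Section 13.3 gives 64 per arm for the primary endpoint (difference 0.8 mm, SD 1.6 mm, two-sided 5%, 80% power). By the normal formula, n = 2 × (1.960 + 0.842)² × (1.6/0.8)² = 62.8, so 63 per arm. The t-test needs 63.8, so 64, with power 80.1%. The figure reproduces and this point does not change it. No sample size or power is stated for miRNA. The only miRNA performance figure for this type of nodule, in the biomarker rationale, is 24 of 27 people with GGO testing positive: 24/27 = 88.9% (exact 95% CI 70.8% to 97.6%).

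**2. The definitions side by side.**

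| | Sections 1.2 and 3 | Section 8.2, miRNA paragraph |
|---|---|---|
| Outcome | the signature after treatment | agreement of the test with LDCT; prediction of response |
| Contrast | aspirin against placebo | none stated |
| Link to nodules | correlation with diameter change | CT as reference standard |
| Time point | after treatment | none stated |

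**3. Accuracy at baseline.** Inclusion criterion 4.1.4 requires a subsolid nodule, so among eligible participants there are up to 128 reference-positives and 0 reference-negatives.

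- Specificity = true negatives / all reference-negatives = 0/0, which cannot be estimated.
- Accuracy = (true positives + true negatives) / 128 = true positives / 128, which is simply sensitivity.

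Within the trial, reference-negatives for subsolid nodules could arise only at month 12, in people whose subsolid nodules have gone. By then the samples come from a population of which half (64 of 128) was assigned to aspirin.

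**4. Accuracy at month 12, if the aspirin arm is included.** Let f be the share of test-positive aspirin participants whose test turns negative while the nodule is still on CT. The documents give no value for f, so a range is shown. Assume 64 per arm, no dropout, all nodules persisting and placebo sensitivity staying at 88.9%.

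- Aspirin-arm sensitivity = (24/27) × (1 − f)
- Both arms pooled = the mean of the aspirin-arm value and 88.9%

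| f | Aspirin arm | Both arms pooled |
|---|---|---|
| 10% | 80.0% | 84.4% |
| 25% | 66.7% | 77.8% |
| 50% | 44.4% | 66.7% |

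Under 1.2 and 3 these changes are the effect to be measured. Under 8.2 they would appear as false negatives.

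**5. Where step 4 does not apply.** In pre-treatment samples f = 0, so aspirin cannot lower sensitivity. If nodules resolve along with the score, the loss shrinks. With f = 50% and half the aspirin-arm nodules gone, all among test-negatives, sensitivity is 0.444/0.50 = 88.9% again.

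**The case against.** The strongest reply is that the plan already covers the question. The opening line of 8.2 promises the effects of aspirin on the listed endpoints and refers to 13.5. The model there has arm and visit as fixed effects and an identity link for normal data, so it could take a continuous miRNA score. Section 9.1 also foresees correlating miRNA quantities with radiological parameters. This stands in part: an arm comparison is possible under the text, and one should not conclude that the plan rules it out. But 13.5 never names a miRNA variable, it lists a month-6 visit at which miRNA is not measured, and the only definition specific to miRNA is the accuracy one.

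Four stronger readings are tempting, and the documents do not support them:

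- **A true aspirin effect must look like a failing test.** That follows only if accuracy is computed on month-12 samples that include the aspirin arm and the score falls while the nodule persists. Section 8.2 gives no time point.
- **Section 8.2 concerns nodule detection alone.** The same sentence also covers prediction of aspirin response, which is a legitimate separate aim.
- **The plan loses power by comparing test-positive proportions between arms.** Section 8.2 plans no such comparison, so a power contrast against it would say nothing about this trial.
- **miRNA is the leading secondary endpoint.** Sections 1.2 and 3 single it out, but no ranking of secondary endpoints is given.

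**Conclusion.** The point holds as a mismatch between objective and endpoint definition. As written, the miRNA paragraph of 8.2 contains no measure of aspirin's effect on the signature, and 13.5 fills the gap only by implication. That specificity for subsolid nodules cannot be estimated at baseline follows directly from the entry criteria and needs no assumption.

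The month-12 distortion is conditional. The falls in sensitivity of about 9 to 44 percentage points in the aspirin arm (88.9 − 80.0 = 8.9; 88.9 − 44.4 = 44.5 from the rounded values) rest on assumed conversion rates, persisting nodules, no dropout and a starting value from only 27 people. They illustrate the mechanism and are not a forecast.

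The primary endpoint and the sample size are not affected. The change is worth making because a highlighted biomarker question otherwise has no prespecified outcome or contrast.

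**What to change.** Amend 8.2 and 13.5 as follows.

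1. **Effect of aspirin.** Define the miRNA secondary endpoint as the between-arm difference at month 12 in the pre-existing signature risk score, on the continuous scale, with the baseline score as covariate. Name the version of the score before any outcome data are examined. Add the correlation of score change with change in nodule diameter, as 1.2 promises.
2. **Response prediction.** Keep it as a separate analysis using baseline samples.
3. **Nodule detection.** Within the trial, limit it to sensitivity in pre-treatment samples. Claim specificity or overall accuracy only if a source of reference-negatives outside the trial population is named.

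The cost is wording. The baseline and month-12 blood samples and the assays are already planned and the score already exists, so items 1 and 2 and the sensitivity estimate need no extra participants or procedures. Only a claim about specificity would call for additional outside samples or data.
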